12.2.1. EXACT-PRO baseline score at enrolment

An EXACT-PRO baseline score at enrolment will be computed as the mean within-patient score over 7 days, with data present for a minimum of 4 of the 7 days. If fewer than 4 days of data are available, the EXACT baseline score cannot be calculated.

CONFIDENTIAL201112 (EPI-NTHI-001 BOD APA)
Statistical Analysis Plan Amendment 2 Final**12.3. Time between 2 e-diary signals for exacerbations/evaluation of baseline symptom score:**

The minimum duration between 2 e-diary signals with distinct baseline value is 15 days, which is the minimal period for which a new full exacerbation-free baseline can be calculated for the next e-diary episode.

If a new worsening of symptoms occurs between 6 and 14 days after the end of a previous exacerbation, the baseline period used will be the same baseline as the one of the original exacerbation. Therefore, it will last until the daily symptom count score has gone below the baseline symptom score of the previous event.

12.4. Definition of Missed AECOPD visits

Missed AECOPD visits with medical records (dashed boxes 2 and 7 in [Figure 1](#)) will capture:

- an alert from the electronic Diary Card without a site visit but that cannot be discounted as a possible exacerbation signal after reconciliation (detailed in the Study Procedure Manual),

and/or

- an exacerbation reported retrospectively during a scheduled visit clinically documented for which there has not been a corresponding exacerbation visit.

Onset date, recovery date and severity will be retrieved by medical records.

For the analyses not involving the collection of any biological specimen, exacerbations will refer to AECOPD events plus missed AECOPD visits with medical records.

Missed AECOPD visits without medical records, also referred to as Potential AECOPDs, (dashed box 3 in [Figure 1](#)) will capture:

- an alert from the electronic Diary Card, assessed AECOPD during the phone call, without a site visit and without AECOPD medical records.

12.5. Unconfirmed AECOPD event with morning e-diary signal alert notification.

An alert from the electronic Diary Card not confirmed to be an AECOPD after contact by phone call or at the study site.

CONFIDENTIAL201112 (EPI-NTHI-001 BOD APA)
Statistical Analysis Plan Amendment 2 Final**12.6. Grading of severity of an exacerbation**

Severity of exacerbations is defined as per protocol:

- Mild: Worsening symptoms of COPD that are self-managed by the patient.
- Moderate: Worsening symptoms of COPD that require treatment with oral corticosteroids and/or antibiotics.
- Severe: Worsening symptoms of COPD that require treatment with in-patient hospitalisation or home care intervention.

Severity of the exacerbation will not be derived but they will be taken directly from the information entered in the CRF (i.e. Severity of exacerbation will be taken from the investigator conclusion of the exacerbation visit).

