identified by clinical examination and/or corroborative testing. The worsening in respiratory symptoms may or may not warrant a change in underlying therapy and the symptoms will typically resolve over a period of days to weeks" [ERS/ATS Draft Task Force Recommendations, Major Symposium, ERS Scientific Congress Barcelona 2013]. AECOPD are often associated with concurrent deteriorations in pulmonary function and increases in both local and systemic inflammation. Higher exacerbation rates have been related to a faster decline in lung function and are known to have a negative effect on the patient's quality of life. Moreover, frequent exacerbations are associated with significant mortality, particularly if they require hospitalisation. Between 40 - 60% of medical expenditure for COPD is a direct consequence of AECOPD [Cazzola, 2008]. The severity of AECOPD can be graded according to the intensity of medical intervention required (see [Table 2](#)) [Wedzicha, 2007].

Table 2 Classification of severity of AECOPD

Grade	Intensity of medical intervention
Mild	Controlled with an increase in dosage of regular medications
Moderate	Requires treatment with systemic corticosteroids and/ or antibiotics
Severe	Requires hospitalisation

Bacteria, viruses and environmental pollution are also thought to be important causes of AECOPD [[Sapey](#), 2006]:

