6.3.4.1. Overall incidence

The following incidence rates (per patient per year) will be computed, with 95% CIs [using negative binomial regression detailed in section [6.3.4.4](#)]:.

- Confirmed exacerbations (exacerbation events confirmed by the investigator plus missed exacerbation visits with medical records: 5 and 6 dash boxes for the former and 2 and 7 for the latter from [Figure 1](#)).
- Confirmed exacerbations plus potential exacerbations with alert confirmed by phone call/or at the study site (potential exacerbations correspond to 3 dash box in Figure 1).
- Exacerbation events with sputum sample positive for selected pathogens

CONFIDENTIAL

201112 (EPI-NTHI-001 BOD APA)
 Statistical Analysis Plan Amendment 2 Final

The incidence rate of confirmed exacerbations and of confirmed exacerbations plus potential exacerbations confirmed by phone call/or at the study site, with 95% CIs, will be estimated according to COPD severity at enrolment based on GOLD classification [GOLD 2, 3, 4].

The incidence rates of confirmed exacerbations, with 95% CIs, will be also computed by exacerbation severity.

In addition, the incidence rates of confirmed exacerbations, with 95% CIs, will be estimated according to covariates such as sex, country, age at enrolment (below median age or equal to/above median age), smoking status at enrolment (current and former smokers) and number of exacerbations reported in the 12 months prior to enrolment (one, two and equal or above three).

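### By-severity AECOPD results leave out phone-confirmed events without a visit or medical records, so the confirmed-only mild rate and mild share tend to be too low

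*SAP*

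**What the plan says.** SAP 6.3.4.1 defines the main event set as "Confirmed exacerbations (exacerbation events confirmed by the investigator plus missed exacerbation visits with medical records: 5 and 6 dash boxes", with boxes 2 and 7 of Figure 1 for the missed visits. A missed visit therefore counts only if it has medical records. SAP 12.4 carries the restriction beyond incidence: "For the analyses not involving the collection of any biological specimen, exacerbations will refer to AECOPD events plus missed AECOPD visits with medical records". This covers the severity and duration tables in SAP 6.3.5.

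The remaining unvisited events form box 3: "an alert from the electronic Diary Card, assessed AECOPD during the phone call, without a site visit and without AECOPD medical records". SAP 6.3.4.1 gives them a place in a second, wider rate. The breakdown by GOLD grade is planned for both sets: "The incidence rate of confirmed exacerbations and of confirmed exacerbations plus potential exacerbations confirmed by phone call/or at the study site". The breakdown by severity is planned for one set only: "The incidence rates of confirmed exacerbations, with 95% CIs, will be also computed by exacerbation severity".

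On grading, SAP 12.6 has "Mild: Worsening symptoms of COPD that are self-managed by the patient", whereas Protocol Table 2 (section 1.1) has "Controlled with an increase in dosage of regular medications". For missed visits with records, SAP 12.4 says "Onset date, recovery date and severity will be retrieved by medical records". SAP 12.6 takes severity from the investigator's conclusion of the exacerbation visit as entered in the CRF. A box 3 event has neither source.

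**The concern.** Whether an unvisited event is counted depends on whether a record exists, and that is likely to depend on the grade being estimated. Moderate events involve corticosteroids or antibiotics, and severe events involve admission (or, in SAP 12.6, home care). Both normally leave a trace in care records. Self-management is the grade least likely to do so.

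Severity of AECOPD is a secondary objective and endpoint, and Protocol 9.6 asks for incidence of mild, moderate and severe events separately. If mild events are lost more often than the others, the mild rate is low and the severity mix shifts towards moderate and severe. The SAP adds box 3 as a wider rate overall and by GOLD grade, but not in the breakdown where loss related to grade matters most.

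**Working it through.** **Which events enter which result (SAP 6.3.4.1, 6.3.4.3, 12.4)**

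| Event | Overall and by-GOLD rate | By-severity rate, 6.3.5 |
|---|---|---|
| Visit, investigator-confirmed (boxes 5, 6) | yes | yes |
| No visit, medical records (boxes 2, 7) | yes | yes |
| Phone-confirmed, no visit, no records (box 3) | only in the confirmed-plus-potential version | no |

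**Scale of sampling error.** Protocol Table 13 uses a normal approximation with variance Φn/T². For T = 160, n = 160, Φ = 1: 1 ± 1.96 × √160/160 = 1 ± 0.155, that is 0.845 to 1.155. The table gives 0.85 to 1.15, so it reproduces. No figure in the plan is disputed here.

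**Effect on the mild share.** Let m be the fraction of AECOPD with no visit, taken as equal across grades, and r the fraction of those with a record. The captured fraction of a grade is (1 − m) + m × r. None of these inputs is in the documents. The assumptions are a true mix of 40/45/15% mild/moderate/severe and r = 0.8 for moderate and 1.0 for severe.

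With m = 0.25:
- Moderate: 0.75 + 0.25 × 0.8 = 0.95, contributing 0.45 × 0.95 = 0.4275.
- Severe: 0.75 + 0.25 × 1.0 = 1.00, contributing 0.15.

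| r for mild | Mild captured | Mild contribution | Total | Observed mild share |
|---|---|---|---|---|
| 0 | 0.75 | 0.300 | 0.8775 | 34.2% |
| 0.5 | 0.875 | 0.350 | 0.9275 | 37.7% |
| 0.8 | 0.95 | 0.380 | 0.9575 | 39.7% |

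The mild rate itself is low by m × (1 − r): 25%, 12.5% and 5% on the three rows. With r = 0 for mild, the observed moderate and severe shares are 0.4275/0.8775 = 48.7% and 0.15/0.8775 = 17.1%, against 45% and 15%.

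With m = 0.40 and r = 0 for mild: 0.240/(0.240 + 0.414 + 0.150) = 29.9%.

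**Effect on the mild rate against its precision.** This is a separate illustration, with 160 patient-years, Φ = 1.5, a true overall rate of 1.0 per year, 30% mild, and no loss of moderate or severe events. The true mild rate is 0.30, so n = 48 and the 95% half-width is 1.96 × √(1.5 × 48)/160 = 0.104.

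| Mild events lost | Observed mild rate | Shift | Shift ÷ half-width | Observed mild share |
|---|---|---|---|---|
| 10% | 0.27 | −0.03 | 0.29 | 27.8% |
| 30% | 0.21 | −0.09 | 0.87 | 23.1% |
| 50% | 0.15 | −0.15 | 1.44 | 17.6% |

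The fraction lost is the share of mild events with no visit times the share of those with no record. Assuming 10 to 50% for the first and 50 to 100% for the second, it runs from 5% to 50%.

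**The case against.** The strongest reply is that Protocol 3.1.1 already covers these events. When an AECOPD is confirmed but cannot be seen, the site enters it in the subject's medical records file and in the corresponding eCRF section, and gathers what information it can. The same section has severity information collected when an AECOPD is suspected. SAP 12.4 also lists alerts that reconciliation cannot discount, and clinically documented events reported later at a scheduled visit. A reader might infer that missed mild events cannot enter the by-severity rates at all. The documents do not support that: these routes exist, and mild events seen at a visit are counted.

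The reply does not close the gap. If a site's phone note counted as a medical record, box 3 would be almost empty wherever sites complied, yet the SAP gives it its own definition, tabulation and rate. Both 12.4 routes also sit under missed visits with medical records. What counts as a record is not defined in either document, so two analysts could report different mild rates.

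Three further points stand in part:
- Protocol Table 2 does not call mild events self-managed, and SAP 12.6 takes severity from the CRF. This weakens the presumption that mild events leave no record, but it also shows that the two documents differ.
- SAP 6.3.4.3 tabulates the number of box 3 events and the reasons for missing visits, so the loss is not hidden. No planned table links it to severity.
- SAP section 7 limits all analyses to descriptive, supportive or hypothesis-generating use. Requiring documentation for unseen events is also a defensible preference for specificity. Both points lower the stakes but do not remove the asymmetry between grades.

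**Conclusion.** The point holds as a matter of structure and direction. By-severity rates and the severity description exclude box 3, no by-severity version with box 3 is planned, and under the SAP's wording mild events are the most likely to fall there. The confirmed-only mild rate is best read as a minimum.

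The size cannot be derived. The mild rate loses nothing if no mild visit is missed, or if site notes count as records. The 34.2% to 39.7% range for a true 40% rests entirely on the assumed mix, missed-visit fraction and record rates. The low end needs a zero record rate for missed mild events, which is the extreme case. A reader might conclude that the mild rate is known to be materially wrong. The documents support only a likely direction, and only for severity-specific results, because the overall and by-GOLD rates already have a version that includes box 3.

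**What to change.** In SAP 6.3.4.1 and 6.3.5:
- Add by-severity rates and the severity split for confirmed plus potential (box 3) AECOPD. Use severity collected at the contact under Protocol 3.1.1 where available, and otherwise a category of severity unknown. Do not default box 3 events to mild: SAP 12.6 says severity is not derived, and missing records may conceal corticosteroid or antibiotic treatment.
- Present the mild rate as a range. The lower figure is confirmed mild, labelled a minimum. The upper figure is confirmed mild plus box 3 events collected as mild or of unknown severity.

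In SAP 12.4, state whether a site's own note of a phone-confirmed event counts as medical records for boxes 2 and 7. Reconcile the severity wording of SAP 12.6 with Protocol Table 2, since 12.6 says it follows the protocol but is worded differently. Which wording should prevail is not judged here.

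The cost is SAP text and one extra block in existing tables, with no new data. The downside is that the upper figure may include some moderate events whose records were not obtained, so it is a bound and not an estimate.

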 - For each AECOPD: AECOPD visit (within 96 hours of the onset of the symptoms) and follow-up phone call(s) (at least every 2 weeks until the AECOPD has resolved). Follow-up phone contacts will define end of AECOPD.
- **COPD symptoms**
Subjects will be asked to record their COPD symptoms in an electronic Diary Card on a daily basis:
 - Daily in the morning throughout the study: Morning symptoms questionnaire.
 - Daily at bedtime throughout the study: EXACT-PRO (EXAcerbations of Chronic Pulmonary Disease Tool - Patient Reported Outcome) questionnaire.
- **Biological samples:**
 - **Sputum samples** collected at site (spontaneous or induced, as per investigator judgement) will be collected at each study visit at the site (scheduled [stable] visits and AECOPD visits) if, in the opinion of the investigator, it is safe for the subject.

Or

- **Sputum sample collected at subject's home (spontaneous).** Self-collection of the sputum sample will be allowed in specific cases, where the first dose of antibiotics absolutely needs to be taken before an AECOPD visit can take place. This is not allowed at scheduled visits when subject should be in stable condition.

Note: The sputum samples collected during AECOPD should preferably be obtained before administration of the first dose of antibiotics to treat the AECOPD (if applicable).

- **Blood samples** for biomarker testing will be collected at Visit 1 (M0) and Visit 3 (M12).

- **HRQOL assessments**

- Subjects will be asked to complete the COPD assessment Test (*CAT*) at each study visit (scheduled [stable] visits and AECOPD visits).
- Subjects will be asked to complete the St. George's Respiratory Questionnaire for COPD patients (SGRQ-C) at each scheduled (stable) study visit (Visit 1 [Month 0], Visit 2 [Month 6] and at Visit 3 [Month 12]).
- Pre- and post-bronchodilator spirometry assessments will be done for all subjects at Screening Visit (pre-Month 0) and at Visit 3 (Month 12).

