 - In case the AECOPD is confirmed but no AECOPD visit can take place, the site should record the information in the medical records subject files, and in the eCRF in medical records section and obtain all relevant information regarding the AECOPD (hospital record, medical record etc.) and record this in the eCRF.
- If the investigator concludes the subject is experiencing/continuing with the same event for which a visit has been performed already, an AECOPD visit should not take place. Medical treatment should be foreseen according to standard medical practice outside of the study.

During the AECOPD visit, the investigator will confirm the occurrence of the AECOPD based on clinical and medical judgement and based on the Anthonisen criteria and will record its date of onset. The end date of the AECOPD and its severity will be determined/confirmed by the investigator/delegate during (a) follow-up phone call(s), which will take place at least every 2 weeks until the AECOPD has resolved.

If an AECOPD occurs at the time when one of the scheduled [stable] study visits is planned, it should be handled and recorded as an AECOPD visit, with all relevant AECOPD visit study procedures performed and, if possible, the stable study visit should be re-scheduled to a later date, when the subject is stable again and within the time window specified in the protocol.

The investigator/site must engage their best efforts to reach the patients, however, if the site does not succeed in contacting the patient, the reason should be recorded and an explanation given about what occurred. For example, the subject could be hospitalized or could visit a different physician (and in that case medical record should be obtained), or the subject is on holidays or not able to go the site.

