3.1.1.2. Guideline for assessing AECOPD that increase in severity

If an exacerbation starts off as mild, but becomes moderate or severe or starts off as moderate and becomes severe, the exacerbation should be captured as one exacerbation and classified by its highest level of severity.

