^c Significant comorbidities include weight loss, cardiovascular disease, hypertension, gastro-oesophageal reflux disease, osteoporosis/ osteopenia, skeletal muscle wasting and dysfunction, anxiety/ depression and diabetes.

^d To be recorded in the 'Physical examination' section of the eCRF.

^e Only study certified site staff can perform spirometry assessment.

^f Only if no chest X-ray is taken within the previous 3 months.

^g Sputum can be collected spontaneously or can be induced, as per investigator judgement. Sputum sampling should only be done if, in the opinion of the investigator, it is safe for the subject.

^h Non-serious AEs will be recorded in the eCRF and will not be entered into the safety database.

ⁱ **Refer to Table 10 for description of which AE/SAEs are collected in this study.**

^j Physical examination (Visit1-3) should be done only if necessary by the investigator or delegate.

Table 5 presents the list of study procedures for AECOPD visits.

Table 5 List of study procedures for AECOPD visits

Type of contact	AECOPD Visit	End of AECOPD phone call(s)
Time point	within 96 hours of onset symptoms	at least every 2 weeks as of AECOPD visit until AECOPD has resolved ⁱ
Record date of visit	•	
Physical examination ^j	•	
Urine Pregnancy Test	•	
Chest X-rays/pneumonia confirmation ^j	•	
Confirm AECOPD and record its start date	•	
Record current medication for AECOPD	•	
Record healthcare resource utilisation	•	
Record additional COPD treatments prescribed by primary and secondary care physicians		•
Sputum sampling ^k	•	
HRQOL questionnaire:		
CAT	0	
Record AECOPD severity ^m	•	•
Record AECOPD end date		•
Record Adverse Events (AEs)* ⁿ	•	•
Record serious adverse events (SAEs) ⁿ	•	•

• is used to indicate a study procedure that requires documentation in the individual eCRF.

ⁱ End of AECOPD phone calls/ visits should be scheduled at least every 2 weeks, until the AECOPD has resolved. Only the last phone call will be recorded in the eCRF as the end of the AECOPD phone call. All intermediate calls should be recorded on source documentation.

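### SAP 12.6 points to the exacerbation visit for the severity of visited AECOPD events, while the protocol confirms severity at the follow-up calls at the highest grade reached; if the visit-time entry is used, events that worsen later would be under-graded

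*SAP*

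**What the plan says.** **Protocol.** Section 3.1.1 places the decision on severity after the visit: "The end date of the AECOPD and its severity will be determined/confirmed by the investigator/delegate during (a) follow-up phone call(s"), repeated until the event resolves. For an event that begins at a lower grade and worsens, section 3.1.1.2 says "the exacerbation should be captured as one exacerbation and classified by its highest level of severity". Table 5 in section 6.3 marks severity for eCRF entry in two columns, the AECOPD visit and the end-of-AECOPD call. A footnote to that table adds: "Only the last phone call will be recorded in the eCRF as the end of the AECOPD phone call". Section 6.4.3.11 has severity and end date recorded for every confirmed event and refers to 3.1.1.1 and 3.1.1.2. The visit itself is early. Section 3 describes it as "AECOPD visit (within 96 hours of the onset of the symptoms").

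**SAP Amendment 2.** Section 12.6 opens with "Severity of exacerbations is defined as per protocol". It then states "Severity of the exacerbation will not be derived but they will be taken directly from the information entered in the CRF", and explains in brackets that "Severity of exacerbation will be taken from the investigator conclusion of the exacerbation visit". Section 12.4 gives a different source for missed AECOPD visits with medical records (boxes 2 and 7 of Figure 1), whose severity comes from those records. Section 12.1 uses the follow-up calls to fix recovery and does not mention severity there. Section 9 lists no changes from the planned analyses.

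**The concern.** The severity scale in protocol Table 2 depends on the care an event turns out to need, and severe means hospitalisation. A visit held in the first four days can precede that care. A programmer who follows SAP 12.6 and finds two severity entries for a visited event (boxes 5 and 6) would take the one from the visit. An event graded mild or moderate there and hospitalised a week later would stay at the lower grade, contrary to protocol 3.1.1.2.

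Severity stratifies many of the planned results:

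- pathogen proportions by AECOPD severity, a secondary objective (SAP 6.3.2);
- severity-specific incidence rates (6.3.4.1 and 6.3.4.2);
- duration (6.3.5), CAT (6.3.6) and healthcare use (6.3.8).

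Three side effects would follow. Healthcare use by severity could show hospital admissions under events graded mild or moderate. Section 6.3.5 assigns an average length by severity grade when an end date is unknown, so a wrong grade would carry into days in exacerbation. The severity-specific rate of confirmed exacerbations would also mix two definitions: an early grade for visited events, and a grade from the medical record, which can cover the whole event, for missed visits.

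**Working it through.** **Comparing the rules**

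| | Protocol | SAP 12.6, read literally |
|---|---|---|
| When severity is settled | Follow-up calls, until resolution | Exacerbation visit |
| Event that worsens | Highest level reached | No rule; not derived |
| Entries available | Visit and last call (Table 5) | One, from the visit |
| Missed visit with records | Records obtained (3.1.1) | Medical record (12.4) |

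The current SAP nowhere states the highest-level rule or the use of the call-based grade.

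**Direction.** Let V be the grade at the visit and P the highest grade over the event. Since P is a maximum that includes V, V ≤ P always. Using V can only lower the severe count and can only raise the mild count. The moderate count can move either way, because it gains from severe and loses to mild. The total number of events does not change.

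**The plan's own figures.** No stated figure depends on severity, so there is none at issue to reproduce. For scale, protocol 9.2 has 200 × 0.80 = 160 evaluable subjects. Table 13 at T = n = 160 and Φ = 1 gives 1 ± 1.96 × √160/160 = 1 ± 0.155, that is 0.85 to 1.15, as printed. For sputum, 200 × 0.9 × 0.8 = 144, given there as around 140.

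**Illustration.** None of the following assumptions is in the documents:

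- 160 patient-years with one event each, all with a visit;
- a peak-grade split of 20% severe, 60% moderate and 20% mild, that is 32, 96 and 32 events;
- a fraction f of severe and of moderate events that reaches that grade only after the visit, each moving down one grade.

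Then severe = 32(1 − f), moderate = 96(1 − f) + 32f and mild = 32 + 96f, each divided by 160.

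| f | Severe/yr | Moderate/yr | Mild/yr |
|---|---|---|---|
| 0 (peak grade) | 0.20 | 0.60 | 0.20 |
| 10% | 0.18 | 0.56 | 0.26 |
| 30% | 0.14 | 0.48 | 0.38 |
| 50% | 0.10 | 0.40 | 0.50 |

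The severe rate is multiplied by (1 − f) whatever the split. With 10% severe it falls from 0.10 to 0.09, 0.07 or 0.05 at f = 10%, 30% or 50%. With 30% severe it falls from 0.30 to 0.27, 0.21 or 0.15.

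**Against sampling error.** With the Table 13 variance at Φ = 1, a severe rate of 0.20 has a 95% half-width of 1.96 × √32/160 = 0.069. The shortfalls of 0.02, 0.06 and 0.10 are respectively well inside, close to and beyond that half-width.

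**Samples.** With 140 AECOPD samples and 20% severe, 140 × 0.20 = 28. At f = 10%, 30% and 50%, 28f = 2.8, 8.4 and 14 samples would be analysed under a lower grade.

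**The case against.** The best counter-argument is that SAP 12.6 may already mean the final grade. It refers to the investigator's conclusion as entered in the CRF, and elsewhere in the protocol conclusion is the name of a closing eCRF item (screening conclusion, study conclusion). Protocol 6.4.3 groups its procedures under the AECOPD visit, yet 6.4.3.11 within it covers both severity and the end date, and Table 5 has the end date recorded only at the calls. So the exacerbation visit in SAP 12.6 could mean the whole episode record. On that reading sites apply 3.1.1.2 when they enter the data, the stored value is already the highest grade, and declining to derive severity does no harm. Table 5 also does not show whether there are two stored fields or one that is updated.

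This stands to the extent that under-grading is conditional. It does not remove the conflict. SAP 12.1 separates calls from visits and omits severity from the sentence on the calls, where the matching protocol sentence includes it. The statement that severity follows the protocol cannot carry the missing rule either: the grade wording in 12.6 already differs from protocol Table 2 (for example, home care intervention appears under severe only in the SAP), and those passages must also be reconciled.

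Two further limits stand. A reader might infer that the visit is the SAP's only source of severity. It is not, because missed visits use medical records, and protocol 3.1.1 mentions hospitalisation as one reason a subject may not be reached, so some severe events may be graded by that route. And all analyses are descriptive (SAP section 7).

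**Conclusion.** The inconsistency is real and in the current text. For visited events, SAP 12.6 names a source that, taken literally, ignores the protocol's confirmation at the calls and its highest-level rule. If the visit-time entry is used, any error runs one way: severe events are undercounted and mild ones overcounted in every result by severity. Pathogens by severity is the most exposed result, since AECOPD-visit sputum comes from visited events. For incidence the effect is diluted by the events in boxes 2 and 7.

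A reader might go further and infer that late-worsening events are under-graded in this study, by some definite amount. The documents do not support that. They do not show the eCRF, so the entry used may be the final one. They also give neither the share of events that escalate nor the severity split. The 10% to 50% range above is assumed, and the proportional loss in the severe rate simply equals the assumed f. Overall incidence and the unstratified primary proportions are unaffected. This is more than a missing detail, because the literal rule contradicts the protocol and has a known direction of bias, but it does not touch the main primary estimates.

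**What to change.** Replace the last sentence of SAP 12.6 with a rule that matches protocol 3.1.1.2. The analysed severity is the final grade confirmed at the end-of-AECOPD call, meaning the highest level recorded across the AECOPD visit and that call. For missed AECOPD visits it is the grade in the medical record. Name the eCRF field that holds it. If the visit and call entries are stored separately, tabulate the events whose grade changed between them, which would also supply the escalation share that is now unknown. If the visit grade is what the sponsor intends, say so in SAP section 9 as a departure from the protocol, with the reason.

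The cost is one sentence and, if there are two fields, a maximum over them plus one small table. Protocol Table 5 already calls for both entries, so no new data are needed.
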